Safety and laboratory assessments, samples for dupilumab concentration and anti-drug antibody (ADA) response to dupilumab, neutralizing antibody (Nabs), and efficacy assessments will be performed or collected at specified time points throughout parts A and B of the study. Patients will also undergo sparse blood sample collection for characterizing the repeat-dose trough concentrations of dupilumab in serum during part B.

Patient participation in the genomics sub-study in parts A and B is optional. Samples for DNA analysis will be collected from patients whose parents or legal guardians agree to enroll them in the optional sub-study and sign a separate genomics sub-study informed consent form (ICF).

Patient participation in the vaccination sub-study in part B is optional. Patients' parents or legal guardians who plan to have their children vaccinated during the study and agree to enroll them in the optional sub-study, will sign a separate vaccination sub-study ICF for the collection of 2 blood samples (one sample will be drawn before administration of the vaccine, and the second sample will be drawn 3 to 4 weeks [maximum 6 weeks] after administration of the vaccine) for assay of vaccine immunoglobulin G (IgG) in serum for each vaccine administered.

Patient participation in a tape-stripping sub-study at selected study sites in part B is optional. Tape stripping samples may be taken for exploratory biomarker analysis from patients whose parent(s) or legal guardian(s) consent for the child to participate in this optional sub-study.

An OLE study (R668-AD-1434) in patients aged 6 months to <18 years old is currently ongoing. Patients who complete the treatment period in either part A or part B may be eligible to enroll in this OLE study in which they will receive treatment with dupilumab.

Study Duration

The duration of the study for a patient in part A is approximately 8 weeks, excluding the screening period (patients would have the option to enroll into an OLE study at week 4), and duration of the study for a patient in part B is approximately 28 weeks, excluding the screening period (patients would have the option to enroll into an OLE study at week 16). A patient cannot participate in both parts A and B of the study.

Population**Sample Size:**

For part A, approximately 40 pediatric AD patients aged ≥ 6 months to <6 years are planned to be enrolled in 4 cohorts as follows:

- Cohort 1A: ≥ 2 to <6 years of age, 3 mg/kg dose, n = 10
- Cohort 1B: ≥ 2 to <6 years of age, 6 mg/kg dose, n = 10
- Cohort 2A: ≥ 6 months to <2 years of age, 3 mg/kg dose, n = 10
- Cohort 2B: ≥ 6 months to <2 years of age, 6 mg/kg dose, n = 10

To ensure adequate representation of patients from all age-groups, a cap will be placed on the number of patients who will be enrolled in each of the dose sub-cohorts (3 mg/kg and 6 mg/kg) as follows:

Cohorts 1A and 1B:

- 2 years to <4 years of age: 7 patients
- 4 years to <6 years of age: 7 patients

Cohorts 2A and 2B:

- 6 months to < 1 year of age: 7 patients
- 1 year to <2 years of age: 7 patients

For part B, approximately 160 pediatric AD patients aged \geq 6 months to <6 years are planned to be randomized. Randomization will be stratified by baseline weight (\geq 5 to <15 kg or \geq 15 to <30 kg), by baseline disease severity (IGA=3, 4), and by region/country (North America, Europe, Japan, and China) in a 1:1 ratio to dupilumab or placebo. To ensure adequate representation of patients from Japan and China, randomization slots will be reserved for patients from these countries in an interactive web response system. The number of patients with moderate AD (IGA=3) will be capped at approximately 40. The dose regimens are dupilumab Q4W tiered fixed-dose regimen (200 mg or 300 mg) or placebo Q4W.

Target Population:	The study population includes pediatric patients with severe AD (part A) or moderate-to-severe AD (part B) aged \geq 6 months to <6 years that cannot be adequately controlled with topical AD medications.
Treatments	Study treatment is administered by study site personnel. Background and rescue treatment are to be applied by the patient's caregiver.
Study Drug Dose/Route/Schedule:	For part A, dupilumab SC, 3 mg/kg for dose cohorts 1A and 2A, and 6 mg/kg for dose cohorts 1B and 2B, given as a single dose on day 1. For part B, dupilumab is supplied in prefilled syringes for SC administration. 
• Patients with a baseline weight of \geq5 kg to <15 kg will receive dupilumab 200 mg SC on day 1 followed by the same dose given SC Q4W through week 12.• Patients with a baseline weight of \geq15 kg to <30 kg will receive dupilumab 300 mg SC on day 1 followed by the same dose given SC Q4W through week 12.
Placebo Route/Schedule:	For part B, 2 matching placebo formulations (without addition of active substance) will be used during the study: 
• placebo matching 200 mg dupilumab formulation• placebo matching 300 mg dupilumab formulation Patients in the \geq 5 to <15 kg weight stratum will receive placebo-matching dupilumab 200 mg SC on day 1 and then Q4W through week 12. Patients in the \geq 15 to <30 kg weight stratum will receive placebo-matching 300 mg Q4W through week 12.

Background Treatment**Dose/Route/Schedule:**

Background treatment is applied by the patient's caregiver. For part B, patients are required to have moisturizers (emollients) applied at least twice daily for at least the 7 consecutive days immediately before randomization (not including the day of randomization). At least 11 of the 14 total applications must be applied for the subject to remain eligible for the study. Patients are to continue to have moisturizers applied throughout the remainder of the study (all 28 weeks where applicable). However, to allow adequate assessment of skin dryness, moisturizers should not be applied for at least 8 hours before each clinic visit. All types of moisturizers are permitted, but patients may not initiate treatment with prescription moisturizers or moisturizers containing additives during the screening period or during the study. Patients may continue using stable doses of such moisturizers if initiated before the screening visit.

For part B, starting on day -14, all patients are required to initiate treatment with low potency TCS using a standardized regimen according to protocol-specified guidelines. A list of steroids that can be used during the study will be provided to the investigators as part of the investigator site binder. Based on investigator discretion, low/mild potency TCS may also be used on areas of thin skin (face, neck, intertriginous, and genital areas, areas of skin atrophy, etc).

Rescue Treatment**Dose/Route/Schedule:**

For parts A and B, medium or high potency TCS, systemic corticosteroids or nonsteroidal immunosuppressants, or TCI may be provided as rescue treatment to study patients at the discretion of the investigator. The use of rescue treatment is only allowed after day 14 of the study in part B. Investigators will be required to perform an Investigator Global Assessment (IGA) prior to starting rescue treatment and will initiate rescue treatment only in patients who either have an IGA score = 4 or have intolerable symptoms.

Endpoints**Primary:**

The primary endpoints in part A are:

- Concentration of total dupilumab in serum over time and PK parameters (summary statistics of drug concentration and PK parameters)
- The incidence and severity of treatment-emergent adverse events (TEAEs) through the end of part A.

The primary endpoint in part B is the proportion of patients with an IGA score of 0 to 1 (on a 5-point scale) at week 16.

The co-primary endpoints in part B (**only in European Union [EU] and EU Reference Market Countries**):

- Proportion of patients with Eczema Area and Severity Index (EASI)-75 ($\geq 75\%$ improvement from baseline) at week 16
- Proportion of patients with an IGA score of either 0 or 1 (on a 5-point scale) at week 16

Secondary:

The secondary endpoints in part A are:

- The incidence of serious adverse events (SAEs) and severe TEAEs to week 4
- Percent change in EASI score from baseline to week 4
- Percent change in SCORing Atopic Dermatitis (SCORAD) from baseline to week 4
- Proportion of patients with an IGA score of either 0 or 1 (on a 5-point scale) at week 4

Immunogenicity will be addressed by the ADA parameters described in the protocol.

The key secondary endpoints in part B are:

- Proportion of patients with EASI-75 ($\geq 75\%$ improvement from baseline) at week 16 (**not applicable for EU or EU Reference Market Countries**)
- Percent change in EASI score from baseline to week 16
- Percent change from baseline to week 16 in weekly average of daily worst scratch/itch numeric rating scale (NRS) score

Procedures and Assessments

Safety and tolerability will be assessed by vital signs, physical examinations, clinical laboratory tests, and clinical evaluations. Parents/caregivers will be asked to monitor all adverse events (AEs) experienced from the time of informed consent until their last study visit.

Serum samples will be collected for assay of dupilumab concentrations, and PK parameters will be calculated using the dupilumab concentration data. Serum samples will be collected for ADA and NAb assessments and biomarker analyses, and research testing. Tape stripping samples (optional) may also be taken for exploratory biomarker analysis at a subset of study sites.

Efficacy will be assessed during the study at specified clinic visits using the investigator-assessed IGA, EASI, SCORAD, and Body Surface Area (BSA) involvement, parent/caregiver-reported worst scratch/itch NRS, skin pain NRS, and parent/caregiver-reported measures of AD symptoms, sleep, and quality of life (QOL).

Statistical Plan

In part A of the study, the sample size of 40 patients was empirically based on the number of patients required to adequately characterize the safety/PK profile in this population.

For part B of the study, it is estimated that a sample size of 160 patients (80 patients per group), at the 2-sided 5% significance level, will provide:

- 88% power to detect a difference of 21.4% between the dupilumab and placebo groups in the percentage of patients who achieve an IGA score of 0 to 1 at week 16, assuming that the percentages are 32.8% and 11.4% for the dupilumab and placebo groups, respectively.
- 99% power to detect a difference of 42.9% in the percentage of patients who achieve an EASI-75 response at week 16, assuming that the percentages are 69.7% and 26.8% for the dupilumab and placebo groups, respectively.

The analyses for parts A and B will be performed separately.

For parts A and B, demographic and baseline characteristics, safety, PK, ADA, and NAb data will be summarized descriptively by treatment group.

For part A, the open-label portion of the study, descriptive statistics of the efficacy endpoints will be summarized. No statistical hypothesis will be tested.

For part B, the efficacy analysis will be performed for the comparisons between the dupilumab treatment groups and the placebo group. Patients will be randomized in a 1:1 ratio, stratified by baseline weight, baseline disease severity, and region/country.

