- 12 The questionnaires will be administered only to those patients and/or parents/caregivers who speak fluently the language in which the questionnaire is presented (based on availability of validated translations in participating countries). It is recommended that the same person complete the questionnaire on behalf of the patient throughout the study.
- 13 Childrens' Dermatology Life Quality Index (CDLQI) for patients ≥ 4 years of age, Infants' Dermatitis Quality of Life Index (IDQOL) for patients <4 years of age, Dermatology Family Index (DFI) to be completed by an adult family member of a child affected by dermatitis.
- 14 Questionnaire will be completed by the parent/caregiver on behalf of the patient. It is recommended that the same person complete the questionnaire on behalf of the patient throughout the study.
- 15 Patients will be monitored at the study site at visits 3, 7, and 11 for a minimum of 2 hours after study drug administration. Vital signs (sitting systolic and diastolic blood pressures, heart rate, respiratory rate, and body temperature) and AE assessments will be done at 30 minutes (± 10 minutes) post-injection, and then at 2 hours (± 15 minutes) post-injection.
- 16 Samples will be collected before the injection of study drug.
- 17 TB testing will be performed on a country-by-country basis, according to local guidelines, if required by regulatory authorities or ethics boards.
- 18 Optional collection of blood for assay of vaccine IgG in serum for each vaccine administered. The first sample should be drawn within 6 weeks prior to vaccination, and the second sample should be drawn 3 to 4 weeks (maximum 6 weeks) after vaccination. Vaccinations should be performed in compliance with the patient's recommended immunization schedule. Blood collections should be conducted at regularly scheduled study visits but, if this is not feasible, samples can also be drawn at unscheduled visits.
- 19 Samples to measure functional dupilumab concentration and biomarkers will be collected prior to injection of study drug.
- 20 Samples to be collected prior to injection of study drug. Patients who are ADA positive at their last study visit (early termination, or end of study) and who do not participate in the OLE may be considered for follow-up based on the overall clinical presentation at that time. Patients who are considered for follow-up may be asked to return to the clinic to have additional samples collected for analysis.

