### **3.3. The Pharmacokinetic Analysis Set (PKAS)**

The PK analysis set includes all randomized patients who received any study drug and who had at least one non-missing drug concentration result following the first dose of study drug.

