## **5.8. Analysis of Pharmacokinetic Data**

The following analyses will be conducted:

- Descriptive statistics of functional dupilumab concentrations in serum at each sampling time by dose
- Graphical presentations of median and mean (+/- SD) functional dupilumab concentration in serum vs nominal time profiles
- Graphical presentations of individual functional dupilumab concentration in serum vs actual sampling time profiles
- Assessment of the impact of anti-drug antibodies on functional dupilumab concentrations in serum.

No formal statistical analysis will be performed.

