### **6.4. Analysis Visit Window**

Data analyzed by-visit-analysis (including efficacy, laboratory data, visit sign, ECG, ADA) will be summarized by the study scheduled visits described in the study protocol and SAP "Schedule of Events". The analysis visit windows will be exhaustive so that all available values obtained from unscheduled visits, early termination (ET) visit have the potential to be summarized. No analysis visit windows will be applied for the study scheduled visits.

The analysis visit windows are created per study Schedule of Events (SOE) table for each parameter and will be applied if the data from study scheduled visits are unavailable. The following general rules will be applied to unscheduled visit and/or early termination (ET) visit mapping for each parameter.

1. If ET visit falls in an analysis window which already has no missing observed value of this parameter from the scheduled visit, ET will be mapped to the next scheduled visit.
2. If both ET visit and unscheduled visit of the same parameter are available in the same analysis visit window, only ET visit will be mapped.
3. If multiple unscheduled visits of the same parameter are available in the same analysis visit window, the unscheduled visits will be mapped using the following rules:

- a. The closest unscheduled visit from the target day will be selected.
- b. If multiple unscheduled visits exist on the same day, the first unscheduled visit will be used.

4. If mapping distance is greater than 2 weeks, the unscheduled visit will not be mapped.

Unscheduled visits and early termination (ET) visit will be mapped per the following analysis visit windows based on the visit schedule of each parameter as per [Appendix 3](#).

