**Table 4: Analysis Visit Window for Safety labs, Vitals, PK and Biomarkers**

Visit from SOE	Target Study Day in Part B a	Vital signs	Physical examination, ECG, Height, Weight	Lab*	PK, ADA	TARC#, Serum Immunoglobulin profiling, antigen-specific IgE
Baseline	1	≤1	≤1	≤1	≤1	≤1
Week 1	8	[2, 11]				
Week 2	15	[12, 22]				
Week 4	29	[23, 43]		[2, 71]	[2, 43]	[2, 71] #
Week 8	57	[44, 71]			[44, 71]	
Week 12	85	[72, 99]			[72, 99]	
Week 16	113	[100, 127]	[2, 155]	[72, 155]	[100, 127]	[72, 155]# [2, 155]
Week 20	141	[128, 155]			[128, 169]	
Week 24	169	[156, 183]				
Week 28	197	>= 184	>= 156	>=156	>= 170	>= 156

\*Hematology and Blood Chemistry only.

#Only for TARC which was collected at baseline, Day 29, Day 113/EOT and Day 197/EOS.

Note that both scheduled and unscheduled measurements will be considered for determining abnormal/PCSV values for laboratory, vital signs or ECGs as well as the baseline values.

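### SAP 6.4 and Table 4 let unscheduled and early-termination PK samples taken 1–14 days after a dose enter visit summaries otherwise made of pre-dose troughs

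*Protocol*

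**What the plan says.** **Purpose and timing.** The Protocol Synopsis (Study Design, Parts A and B) states: "Patients will also undergo sparse blood sample collection for characterizing the repeat-dose trough concentrations of dupilumab in serum during part B". Section 3.1 says much the same. After day 1, drug is "followed by the same dose given SC Q4W through week 12" (Synopsis, Treatments), which Protocol Table 2 places on days 1, 29, 57 and 85. Footnote 19 to that table fixes the order at dosing visits: "Samples to measure functional dupilumab concentration and biomarkers will be collected prior to injection of study drug". PK is scheduled at baseline and Weeks 4, 8, 12, 16, 20 and 28. It is also drawn at unscheduled and ET visits; footnote 21 foresees extra samples around suspected serious events.

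**Assignment to visits.** SAP 6.4 makes its windows exhaustive, so that "all available values obtained from unscheduled visits, early termination (ET) visit have the potential to be summarized". Scheduled visits are not windowed, and the windows act only where the scheduled value is unavailable. Rule 1 moves an ET value to the following scheduled visit if its own window already holds a scheduled value. Rule 4 leaves an unscheduled visit unmapped if it lies more than two weeks from target. The PK and ADA column of SAP Table 4 gives the study-day ranges.

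**Summary.** SAP 5.8 plans "Descriptive statistics of functional dupilumab concentrations in serum at each sampling time by dose". SAP 4.6 names Ctrough and Ctrough,SS as parameters that may be reported. The PK analysis set (SAP 3.3) is "all randomized patients who received any study drug and who had at least one non-missing drug concentration result following the first dose". None of these sections sets a condition on time since the last dose.

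**The concern.** Midpoint windows around a target day suit a measure that drifts slowly between visits. A drug concentration does not: it falls to its lowest point just before an injection and then rises. The scheduled Week 4, 8 and 12 samples sit at that low point, and the window extends equally far past it. A sample drawn a week after the injection therefore represents a different part of the dosing interval, yet it is summarised under the same visit label.

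At stake is how the by-dose concentration summary is read. Protocol 1.2.2 chose the two weight tiers by comparing simulated steady-state troughs with those in adults, so readers will look to the Week 4 to Week 16 values for the observed counterpart. Post-dose values push that summary upward.

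**Working it through.** **1. Reproduce the plan's windows.** Target day = 7 × week + 1, giving 29, 57, 85, 113, 141 and 197 for Weeks 4, 8, 12, 16, 20 and 28. The upper edge is the midpoint between neighbouring targets: (29+57)/2 = 43; (57+85)/2 = 71; (85+113)/2 = 99; (113+141)/2 = 127; (141+197)/2 = 169. These match the PK column of SAP Table 4.

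**2. Overlay the dosing days (nominal days 1, 29, 57, 85).**

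| Visit | PK window | Dose inside | Post-dose days | Share of window | Days since that dose |
|---|---|---|---|---|---|
| Week 4 | 2–43 | 29 | 30–43 | 14 of 42 | 1–14 |
| Week 8 | 44–71 | 57 | 58–71 | 14 of 28 | 1–14 |
| Week 12 | 72–99 | 85 | 86–99 | 14 of 28 | 1–14 |
| Week 16 | 100–127 | none | none | none | 15–42 after day 85 |

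A scheduled trough is about 28 days after the preceding dose.

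**3. Apply the two-week cap (unscheduled samples only).** For Week 4 it leaves days 15–43, which is 29 days, and 14 of them are post-dose. For Weeks 8 and 12 the window edges lie at most 14 days from target (71 − 57 = 14; 99 − 85 = 14), so nothing is removed. No post-dose day is excluded at any of the three visits.

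**4. Apply ET rule 1.** Take a child whose scheduled sample for the current window is present and who then leaves the study:

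- ET on day 36 maps to Week 8; days since dose 36 − 29 = 7
- ET on day 64 maps to Week 12; 64 − 57 = 7
- ET on day 92 maps to Week 16; 92 − 85 = 7

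Each is 21 days from its new target (57 − 36, 85 − 64, 113 − 92), but the cap is not worded for ET visits. The child has left, so no later scheduled sample displaces the value. This is also the only way a post-dose value of this kind reaches Week 16.

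**5. Direction and rough scale (assumptions).** The documents give no half-life. Assume simple halving every 7 to 21 days. Relative to the level at the end of the same 28-day interval:

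- 7 days after the dose (21 days early): 2^(21/7) = 8; 2^(21/14) = 2.8; 2^(21/21) = 2
- 14 days after the dose (14 days early): 2^(14/7) = 4; 2^(14/14) = 2; 2^(14/21) = 1.6

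One such value among n otherwise similar troughs raises the mean by (r − 1)/n. With n = 40 in a tier (assumed: an even split of the planned 80 per arm), that is 0.6/40 = 1.5% at r = 1.6 and 7/40 = 17.5% at r = 8. This ignores absorption and target-mediated clearance, so only the upward direction is firm.

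**6. Allowable Week 16 interval.** Weeks 12 and 16 each carry ±3 days in Protocol Table 2. Shortest: (113 − 3) − (85 + 3) = 22 days. Longest: (113 + 3) − (85 − 3) = 34 days. Samples that comply with the protocol therefore span 28 ±6 days.

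**The case against.** The best defence is that this is a by-visit concentration table, not a trough table. SAP 5.8 speaks of each sampling time, Protocol 8.3 defines the variable as concentration at each time point, and the schedule includes Weeks 20 and 28, which are 8 and 16 weeks after the last planned dose. Ctrough and Ctrough,SS are only possible outputs. Scheduled samples always take precedence, so an unscheduled value enters only when the same child's scheduled sample is missing. PK is descriptive and among the other objectives. Medians and quartiles are standard output and resist a few high values. Individual profiles are plotted against actual time, and Protocol 9.5.4 allows a separate population analysis.

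All of that stands as a limit on size. It does not rescue the rule: whatever the table is called, its scheduled Week 4, 8 and 12 values are pre-dose, and the mapping places a level of known, different timing beside them.

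A reader might also infer that Table 4 is what keeps samples from children who have stopped dosing. It is not. Those are mostly correctly scheduled samples, retained because Protocol 5.4.2 asks such children to attend remaining visits and SAP 3.3 requires only one dose and one later result. For a by-visit concentration summary, that is a defensible choice. It needs attention only where a value is reported as Ctrough or Ctrough,SS.

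**Conclusion.** The defect is real and modest. As written, SAP 6.4 and Table 4 can put levels 1–14 days after a dose into the Week 4, 8 and 12 PK summaries, and ET rule 1 can do the same at Weeks 8, 12 and 16. The bias from these samples is upward. This follows from the stated windows and the nominal dosing days and does not depend on any assumed half-life.

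The size cannot be fixed from the documents, which give neither a half-life nor a count of affected children. The percentages above are illustrations per child. Few children are likely to be involved.

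A reader might go further and infer that the dose choice or the trial's conclusions are put in doubt. The documents do not support that: the tiers were selected from population PK simulation, no formal PK test is planned, and no efficacy or safety conclusion changes. Nor does the SAP say that Ctrough,SS will be read from the Week 12 or Week 16 means.

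**What to change.** In SAP 6.4 and Table 4, exclude PK from the unscheduled/ET calendar mapping and from the ET roll-forward. Split the shared PK and ADA column so that ADA is untouched. In SAP 5.8, state that:

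- Weeks 4, 8 and 12 use samples drawn before that visit's injection and within the protocol visit window.
- Week 16 uses samples about 28 ±6 days after the Week 12 dose. A narrower 28 ±3 days would drop samples that comply with both visit windows.
- Weeks 20 and 28 use the scheduled follow-up samples.
- All other samples go to listings and to the actual-time plots already planned.
- Any reported Ctrough or Ctrough,SS is based on children who received the planned preceding doses. The by-visit concentration summary in all dosed children is kept alongside, with scheduled samples from children no longer dosed remaining in it.

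The cost is SAP wording and one derivation. The sample and injection dates and times needed are already used for baseline (SAP 6.1) and for the actual-time plots (SAP 5.8). The downside is slightly fewer values per visit.
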